The duration of an individual subject's participation in this study will be carried out over six months. Enrollment completion will be scheduled for April 2019.

e) Study Endpoints

	Protocol Title:	Post Excision/Mohs Fractional CO2 Resurfacing: A Quantitative and Qualitative Scar Analysis Study
	Principal Investigator Name/Contact Info:	[name] [contact]
	Primary Contact Name/Contact Info	[contact] (office) [contact]
	Date Revised:	2/27/2019
	Study Number:	IF# 2430986 HS# 14-00132 GCO# 14-0387

For primary end point refer to pg.17 , section 7.2.2.1 and for secondary end point refer to pg. 17, section 7.2.2.2

f) Procedures Involved in the Human Research

All patients participating in this investigator initiated split-scar study will receive ablative fractional resurfacing with the Deep and Active FX™ platforms of the Lumenis Ultrapulse CO2 laser. The settings for interventions of scars on the face with the Deep platform will be 15% coverage, 15mJ at 150 Hz and 15% coverage, 12.5 mJ at 150 Hz for off the face. The Active platform settings will be 90 mJ with a density of 3 for the face and 70 mJ and a density of 2 for off the face. The DeepFX™ platform will be applied to the scar prior to the ActiveFX™ platform. Half of the excision scar will be treated with the appropriate settings and half will go untreated. Subjects will be randomized to receive laser intervention at the time of the excision, ten days post-op or 8 weeks post-op. There will be a total of 15 subjects in each study group. Each study group will consist of 5 subjects with excisions on the face, 5 subjects with excisions on the trunk and 5 subjects with excisions on the extremities. General wound care for post surgical excision and laser therapy will include a topical antibiotic cream as well as a topical skin moisturizer and gauze dressing.

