The screening visit will consist of reviewing inclusion/exclusion criteria and obtaining informed consent. There will be a total of 7 study visits to include the day of the excision, post-op day number 10 for suture removal as well as laser therapy if the subject has been randomized to that intervention group, 4 weeks post-op, 9 weeks post-op and laser intervention for subjects randomized to this time frame for intervention, 12 weeks post-op, 17 weeks post-op and 24 weeks post-op. Each visit will last approximately 30-45 minutes each in which clinical photos of the surgical scar will be taken and any wound care or side effects of the laser therapy or surgery will be addressed. Subjects will have a 3 mm punch biopsy taken from both the treated and untreated half of the scar at the post-op visit that correlates approximately with 8 weeks after having been treated with the laser (weeks 9 for two of the subject groups and week 17 for the final study group). These biopsy samples will be taken for the purpose of analyzing the ultrastructure of the collagen architecture. To evaluate this ultrastructure, confocal microscopy using fractional dimension and lacunarity analysis will be used. Further scar analysis will be performed by H&E staining photographs captured on an Olympus BX51 microscope (Olympus America Inc. Center Valley, PA) equipped with MicroFire 2.2 digital camera (Optronics, Goleta, CA) using PictureFrame 2.0 software at 40X magnification. Image analysis will then be performed using NIH's shareware program, ImageJ and the Scar index will be determined. Subjects will have the option of having the untreated portion of their scar treated at no charge at the end of the study if the subject is satisfied with the results of the study

 Mount Sinai	Protocol Title:	Post Excision/Mohs Fractional CO2 Resurfacing: A Quantitative and Qualitative Scar Analysis Study
	Principal Investigator Name/Contact Info:	[name] [contact]
	Primary Contact Name/Contact Info	[contact] (office) [contact]
	Date Revised:	2/27/2019
	Study Number:	IF# 2430986 HS# 14-00132 GCO# 14-0387

g) Specimen Banking

N/A

h) Data Management and Confidentiality

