All records identifying the subject will be kept confidential and, to the extent permitted by the applicable laws and/or regulations, will not be made publicly available. Only the subject number will be recorded in the CRF, and if the subject name appears on any other document, it must be obliterated before a copy of the document is supplied to the sponsor. Study findings stored on a password protected computer will be encrypted and stored in accordance with local data protection laws. As part of the informed consent process, the subjects will be informed in writing that representatives of the IRB, or regulatory authorities may inspect their medical records to verify the information collected, and that all personal information made available for inspection will be handled in strictest confidence and in accordance with local data protection laws. If the results of the study are published, the subject's identity will remain confidential. Only the investigator will maintain a list to enable subjects to be identified. The biopsy specimens will be sent directly to the dermatopathology lab as per standard operating procedure of the department. The specimens will be analyzed then destroyed immediately as per hospital procedures for disposing biologic waste. Photographs will be taken of the scar. If the scar is present on the face, we will focus the picture in a manner that the subject's facial features are not identifiable to maintain their privacy. These photographs will be labeled with the patient ID number and the date. The pictures will not have any subject's name on them. They will be stored on a password protected computer until the study is over at which time they will be transferred onto a disc or USB drive and stored with the rest of the study documents. We will use the study photographs to study the effects of the laser on scars. The photographs will be used for documentation of the study and for the purpose of being viewed by the blinded third party to evaluate the scars and rate them. The camera will be stored in a locked filing cabinet in the PI's office which has a 24 hour keypad lock. All photos will be deleted from the camera after being loaded on to an encrypted and password protected desktop computer located in the PI's office. Only investigators and co-investigators will have access to the photo files

i) Provisions to Monitor the Data to Ensure the Safety of subjects

N/A

j) Withdrawal of Subjects

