	Protocol Title:	Post Excision/Mohs Fractional CO2 Resurfacing: A Quantitative and Qualitative Scar Analysis Study
	Principal Investigator Name/Contact Info:	[name] [contact]
	Primary Contact Name/Contact Info	[contact] (office) [contact]
	Date Revised:	2/27/2019
	Study Number:	IF# 2430986 HS# 14-00132 GCO# 14-0387

If a patient develops an infection while on the study that is serious, he or she will be terminated from the study. If the infection is not serious, and is mild to moderate in severity, then the patient and the investigator will decide, based on whether the infection resolves and whether it is reasonably related to study drug, whether or not to keep the subject on the study. Severe infections will most likely result in termination from the study.

6) Risks to Subjects

The potential risks of this study include erythema post-laser intervention. Some patients may be at risk for potential pigmentation loss while hyperpigmentation can also be a risk; however, laser settings will be adjusted according to the particular area of the body being treated. In addition Fitzpatrick skin types III-V will be excluded from the study in order to minimize this risk. Common minor side effects may include crusting, mild swelling, redness or brown discoloration at the intervention site. In rare cases, hypertrophic scarring or infection may occur. The potential risks of having a biopsy include pain, local swelling, bleeding and/or infection. A small scar may result at the biopsy site. To minimize the appearance of scarring from the biopsy the size of the punch biopsy will be limited to 3 mm.

7) Provisions for Research Related Injury

In the event of related harm or injury the patient will be clinically evaluated by the treating physician. If harm is deemed to have occurred the patient will be triaged and treated in clinically standard treatment protocols. In the case of worsening scar then may consider other modalities (e.g. surgery with a z plasty, dermabrasion, intralesional kenalog, other lasers) or discoloration (other lasers to correct color or topical therapies).

8) Potential Benefits to Subjects

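### Protocol 5j ends follow-up after a serious infection, a listed laser risk, before the supplied SAP's only preference and MMSS rating at 6 months: a minor gap, cheap to close

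*Protocol*

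**What the plan says.** Protocol 5j (Withdrawal of Subjects) has a mandatory and a discretionary part.

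- Serious infection: "If a patient develops an infection while on the study that is serious, he or she will be terminated from the study".
- Mild to moderate infection: patient and investigator decide, looking at whether it resolves and "whether it is reasonably related to study drug, whether or not to keep the subject on the study". The only study treatment is the laser, so I read study drug as the laser.

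Section 6 (Risks to Subjects) places infection among the laser side effects: "In rare cases, hypertrophic scarring or infection may occur". It names a second source as well: "The potential risks of having a biopsy include pain, local swelling, bleeding and/or infection".

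Protocol 5f sets the timing: "Subjects will be randomized to receive laser intervention at the time of the excision, ten days post-op or 8 weeks post-op". There are 15 subjects per timing group, and half of each scar is left untreated. The last visits are at "12 weeks post-op, 17 weeks post-op and 24 weeks post-op", and the biopsies of both halves fall at "weeks 9 for two of the subject groups and week 17 for the final study group".

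The SAP (Statistical analyses) asks for the subject's preference and the blinded physician's MMSS once, 6 months after surgery. It takes the biopsies after those ratings, which differs from 5f. It names a paired t-test, with no analysis set and no rule for subjects who leave early.

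**The concern.** A subject whose lasered half becomes seriously infected leaves the study before anyone records which half looks better. The split-scar design does not protect against this, because termination removes both halves of the pair. A poor result for the laser can then drop out of the comparison for a reason the laser itself caused. The discretionary rule adds a second route, since it lets relatedness to treatment bear on whether the outcome is ever seen.

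The loss could also differ between timing groups, and the ideal time to treat is the protocol's secondary objective. In the immediate group every wound infection follows the laser. In the two delayed groups some come before it.

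Which other data are lost depends on which biopsy schedule is followed. Under 5f, collagen samples already taken are kept, but a biopsy infection at week 9 or 17 can itself end follow-up before week 24. Under the SAP, a terminated subject loses the collagen data too.

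**Working it through.** **Inputs from the documents.** Three timing groups, each with 5 face, 5 trunk and 5 extremity subjects: 3 × (5 + 5 + 5) = 45, which matches the planned enrolment. No infection rate, effect size, SD or dropout rate is given.

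**Assumptions.** Termination rate r = 1% or 2%, with 5% as a deliberately high value. Net preference among completers (laser-better minus untreated-better) d = +20 points. Mean net preference of the lost subjects m, from −1 (all untreated-better) to +1 (all laser-better).

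**Expected loss.** Expected number = 45r. Chance of at least one loss among n subjects = 1 − (1 − r)^n.

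| r | Expected lost of 45 | At least one of 45 | At least one of 15 |
|---|---|---|---|
| 1% | 0.45 | 36% | 14% |
| 2% | 0.90 | 60% | 26% |
| 5% | 2.25 | 90% | 54% |

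**Pooled shift in net preference.** The full-set value is (1 − r)d + rm, so completers minus full set = r(d − m).

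| r | m = −1 | m = 0 | m = +1 |
|---|---|---|---|
| 1% | +1.2 points | +0.2 | −0.8 |
| 2% | +2.4 | +0.4 | −1.6 |
| 5% | +6.0 | +1.0 | −4.0 |

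The shift is zero at m = d. Without ties, that is an untreated-better share of (1 − 0.20)/2 = 40% among the lost. Above 40% the loss favours the laser; below it, the loss works against the laser.

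**One lost subject, pooled.** Suppose completers are 22 laser-better, 13 untreated-better and 9 equivalent: 9/44 = 20.5%. Restoring the lost subject as untreated-better, equivalent or laser-better gives 8/45 = 17.8%, 9/45 = 20.0% or 10/45 = 22.2%.

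**One lost subject in a group of 15.** Suppose 7, 4 and 3: 3/14 = 21.4%. Restored: 2/15 = 13.3%, 3/15 = 20.0% or 4/15 = 26.7%. The adverse case moves the result by 8.1 points, against 2.7 when pooled.

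**MMSS difference.** Shift = (k/45) × gap, where k is the number lost and gap is the completer mean minus the mean of the lost, in SD of the paired difference. One lost with a gap of 1 SD gives 0.02; two lost with a gap of 2 SD gives 0.09. The standard error is 1/√45 = 0.149 SD. Five lost with a gap of 2 SD would give 0.22, so calling the shift small depends on infection being rare.

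**The case against.** The strongest reply is that this hardly matters. Section 6 calls laser infection of any severity rare, and only a serious one forces termination. At 1% there is a 64% chance that nobody in the trial is lost, and an 86% chance in any one group. The largest shifts need every lost subject to favour the untreated half. This stands, and it is why the point is minor. On the other side, discretionary removals and infections from excision or biopsy add to the count, and no document gives a rate.

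A reader might infer that 5j biases the trial towards the laser. The documents do not support that. The rule is not limited to the lasered half or to laser-caused infection, every subject has an excision wound, and both halves are biopsied. Nor does 5j say that a treatment-related mild infection leads to removal, only that relatedness is weighed.

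A reader might also infer that the trial has no follow-up rule for these subjects. That can be said only of the supplied text. Protocol 5e refers to attached sections 7.2.2.1 and 7.2.2.2 for the endpoints, and the protocol also points to attached sections 8 and 9. None of these is supplied. That terminated subjects go unrated is itself an inference from termination with no stated follow-up.

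Photographs are taken at every visit, "for the purpose of being viewed by the blinded third party to evaluate the scars and rate them", so appearance up to termination is kept in a form that could be rated. This partly stands. No supplied rule has them rated after termination, and they cannot give the subject's own 6-month preference.

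Two further objections shape the remedy. Section 7 allows corrective treatment of a worsened scar, so a rating at week 24 may follow rescue and hide the harm. And 5j is a safety rule. Safety can require withholding the laser or a biopsy, but it does not require skipping a question and a visual rating.

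**Conclusion.** The point holds as a minor, cheap improvement. As written, 5j can discard the 6-month preference and MMSS for a reason the laser can cause. The direction is not established.

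At assumed rates of 1–2% the expected loss is 0.45–0.9 of 45 subjects, and the pooled shift in net preference is at most 1.2–2.4 points in the laser's favour, or 0.8–1.6 points against it. The MMSS shift stays below one standard error with one or two losses. Within a timing group of 15 a single loss matters more.

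These sizes rest on the word rare in section 6, on the assumed rates and on the assumed +20 points. The rank of these endpoints is unknown without the attached sections. It would be an over-reading to say that this rule decides the result.

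**What to change.** 1. **Protocol 5j.** Infection leads to treatment, and to withholding the laser or biopsy where clinically needed. The subject is still invited to the week 24 visit for preference and MMSS unless consent is withdrawn.
2. **Analysis.** Include these subjects in the split-scar analysis if they were lasered, and keep them in their randomized timing group.
3. **Rescue.** Record any section 7 corrective treatment given before week 24. For those subjects, add a sensitivity analysis in which the blinded rater scores the last photograph taken before rescue.
4. **Reporting.** By timing group, give the number of infections, the half affected, and whether each came before the laser, after the laser or after biopsy.
5. **Ratings still missing.** Where the infection was confined to one half, show one symmetric sensitivity analysis that counts preference against the infected half, whichever half that is.

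Do not add an analysis that excludes infections up to week 9. It would remove post-laser events in the two early groups but pre-laser events in the third. Nor is there a need for a procedure based on the half assigned to laser: 5f describes randomization of timing, not of halves.

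**Cost.** About two sentences in 5j, a short SAP paragraph, and form items for infection (half and date) and rescue. No visit is added. The downside is that a few infected subjects are followed to week 24, some without laser or biopsy. Protocol 5d schedules the end of enrolment for April 2019, so the change to 5j mainly helps subjects still in follow-up; the reporting is useful whenever the analysis is done.

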6. As per the protocol, the energy setting for treating scars on the trunk and extremity will be reduced to minimize the risk of hyperpigmentation. In addition, subjects with Fitzpatrick skin types III-V will be excluded from the study to minimize the risk of a subject developing hyperpigmentation from the laser intervention.
7. N/A
8. Please see attached protocol page 18 sections 8 and 9.
9. *Should a temporary or permanent suspension of the study occur, the PPHS and IRB will be contacted*

10) Economic Impact on Subjects

Methods of protecting the rights and welfare of subjects include: not preferentially enrolling vulnerable subjects (those that are economically disadvantaged will not be financially induced because no compensation is being provided for participation in this study, providing information to subjects in terms that they can fully understand (the consent form is specifically written such that an individual with a 6th grade education can understand), not exerting any overt or covert coercion, not offering any financial incentives or if offered, not giving an amount that could be considered coercive, and using a consent document that the subject will be asked to sign that is written in the language that the potential subject understands. We will also make sure that the subject understands that there are other options for intervention available to them outside of our study.

11) Payment to Subjects

none

12) Consent Process

 Mount Sinai	Protocol Title:	Post Excision/Mohs Fractional CO2 Resurfacing: A Quantitative and Qualitative Scar Analysis Study
	Principal Investigator Name/Contact Info:	[name] [contact]
	Primary Contact Name/Contact Info	[contact] (office) [contact]
	Date Revised:	2/27/2019
	Study Number:	IF# 2430986 HS# 14-00132 GCO# 14-0387

Consent will be obtained prior to any study procedures and administered by the Principal Investigator or delegates. The consent process will be performed either at the first visit to the study site (not necessarily the first study visit as specified in the protocol) or should the subject prefer to take the consent home to read at leisure, at a subsequent visit. Methods of protecting the rights and welfare of subjects will be taken: not preferentially enrolling vulnerable subjects (those that are economically disadvantaged will not be financially induced because they will be appropriately paid for time and expenses occurred). SOP HRP-090 Informed Consent Process for Research will be followed

13) Process to Document Consent in Writing

The standard PPHS consent template will be used for this research study. The consent process and date that the consent is signed is documented in our source notes.

14) Vulnerable Populations

Indicate specifically whether you will include or exclude each of the following populations:

Include	Exclude	Vulnerable Population Type
	X	Adults unable to consent
	X	Individuals who are not yet adults (e.g. infants, children, teenagers)
	X	Wards of the State (e.g. foster children)
	X	Pregnant women
	X	Prisoners

15) Multi-Site Human Research (Coordinating Center)

N/A

16) Community-Based Participatory Research

N/A

 Mount Sinai	Protocol Title:	Post Excision/Mohs Fractional CO2 Resurfacing: A Quantitative and Qualitative Scar Analysis Study
	Principal Investigator Name/Contact Info:	[name] [contact]
	Primary Contact Name/Contact Info	[contact] (office) [contact]
	Date Revised:	2/27/2019
	Study Number:	IF# 2430986 HS# 14-00132 GCO# 14-0387

17) Sharing of Results with Subjects

During participation in this study, subjects will not be able to access their research records. This will be done to prevent the knowledge of study results from affecting the reliability of the study. Subjects' information will be available should an emergency arise that would require their treating physician to know this information to best treat them. Subjects will have access to their research record and any study information that is part of that record when the study is over or earlier, if possible. The investigator is not required to release to subjects research information that is not part of their medical record. Subjects will always have access to their own clinical medical records while participating in this study.

18) IRB Review History

Approved through 4/15/2019. Seeking continuation for one year

19) Control of Drugs, Biologics, or Devices

Ablative fractional carbon dioxide laser is stored in a combination-locked room accessible only by clinical trials personnel

Note: The IDS has its own forms that must be completed and a review process that must be followed before the IDS representative will sign off on Appendix B for submission to the PPHS.

Post Excision/Mohs Fractional CO2 Resurfacing:
A Quantitative and Qualitative Scar Analysis Study

PI: [name]

NCT02130297

Document Date: 3/9/18

Post Excision/Mohs Fractional CO2 Resurfacing: A Quantitative and Qualitative Scar Analysis Study

PI: [name]

Date: 3/9/18

Statistical analyses

The scars were assessed 6 months after surgery. Each subject was asked if one scar half appeared cosmetically better than the other or if both halves looked cosmetically equivalent. A physician, blinded to treatment, then assessed each half of the scar according to the validated modified Manchester scar scale (MMSS).¹⁶

3mm punch biopsies were then extracted from each scar half and subjected to quantitative scar analysis. Biopsies were fixed in formalin then dehydrated, paraffin-embedded and breadloafed into sections for picrosirius red staining. For analysis of collagen architecture, confocal photographs were captured by a Leica[®] TCSSPMP confocal microscope (Leica Microsystems[®], Wetzlar, Germany) at 1000 fold magnification.¹⁷ Sections were scanned in 1 micron increments for the entire section thickness of 7 microns. Data of frame-mode images were recorded and stored as 512 pixel images. Fractal dimension (F_D) and lacunarity (L) analyses were performed on the confocal images using a previously described methodology.¹⁸

This method for quantitative scar analysis was chosen because confocal microscopy leverages the fluorescence properties of collagen and provides high resolution images of dermal structure. Scar tissue exhibits denser (higher F_D) and more homogenous (lower L) architecture compared with the looser, basket-weave pattern of normal skin. It, therefore, follows that cosmetically superior scar tissue should

closely resemble normal skin, with a lower F_D and higher L. Pairwise t-test comparison was performed using Stata[®] 12 software (StataCorp LLC, College Station, Texas).
